### 11.7.3. Vital Signs

Vital Sign Parameter (Absolute)	Units	Clinical Concern Range	
		Lower	Upper
Systolic Blood Pressure	mmHg	≥ 90	≤ 140
Diastolic Blood Pressure	mmHg	≥ 40	≤ 90
Heart Rate	bpm	≥ 40	≤ 90
Respiration rate	breaths/min	≥ 8	≤ 20
Oral Temperature	°C	≥ 35.5	≤ 37.8

Vital Sign Parameter (Change from Baseline)	Units	Clinical Concern Range	
		Decrease	Increase
Systolic Blood Pressure	mmHg	≥ 40	≥ 40
Diastolic Blood Pressure	mmHg	≥ 20	≥ 20
Heart Rate	bpm	≥ 30	≥ 30

## 11.8. Appendix 8: Abbreviations & Trade Marks

### 11.8.1. Abbreviations

Abbreviation	Description
ADaM	Analysis Data Model
AE	Adverse Event
AIC	Akaike's Information Criteria
A&R	Analysis and Reporting
CDISC	Clinical Data Interchange Standards Consortium
CI	Confidence Interval
CPMS	Clinical Pharmacology Modelling & Simulation
CS	Clinical Statistics
CSR	Clinical Study Report
CTR	Clinical Trial Register
CV b / CV w	Coefficient of Variation (Between) / Coefficient of Variation (Within)
DBF	Database Freeze
DBR	Database Release
DOB	Date of Birth
DP	Decimal Places
pCRF	Paper Case Record Form
EMA	European Medicines Agency
FDA	Food and Drug Administration
FDAAA	Food and Drug Administration Clinical Results Disclosure Requirements
GSK	GlaxoSmithKline
IA	Interim Analysis
ICH	International Conference on Harmonization
IDMC	Independent Data Monitoring Committee
IDSL	Integrated Data Standards Library
IMMS	International Modules Management System
IP	Investigational Product
ITT	Intent-To-Treat
MMRM	Mixed Model Repeated Measures
PCI	Potential Clinical Importance
PD	Pharmacodynamic
PDMP	Protocol Deviation Management Plan
PK	Pharmacokinetic
PP	Per Protocol
PopPK	Population PK
QC	Quality Control
QTcF	Fridericia's QT Interval Corrected for Heart Rate
RAP	Reporting & Analysis Plan
RAMOS	Randomization & Medication Ordering System
SAC	Statistical Analysis Complete
SDSP	Study Data Standardization Plan
SDTM	Study Data Tabulation Model

Abbreviation	Description
SOP	Standard Operation Procedure
TA	Therapeutic Area
TFL	Tables, Figures & Listings

**11.8.2. Trademarks**

Trademarks of the GlaxoSmithKline Group of Companies	Trademarks not owned by the GlaxoSmithKline Group of Companies
HARP	NONMEM SAS WinNonlin

## 11.9. Appendix 9: List of Data Displays

### 11.9.1. Data Display Numbering

The following numbering will be applied for RAP generated displays:

Section	Tables	Figures
Study Population	1.1 to 1.11	N/A
Pharmacokinetic	2.1 to 2.20	2.1 to 2.17
Safety	3.1 to 3.11	N/A
Section	Listings	
ICH Listings	1 to 30	
Other Listings	31 to 46	

### 11.9.2. Mock Example Shell Referencing

Non IDSL specifications will be referenced as indicated and if required example mock-up displays provided in [Appendix 10: Example Mock Shells for Data Displays](#).

Section	Figure	Table	Listing
Study Population	N/A	N/A	N/A
Pharmacokinetic	N/A	N/A	N/A
Safety	N/A	N/A	SAFE_L1

**NOTES:**

- Non-Standard displays are indicated in the 'IDSL / Example Shell' or 'Programming Notes' column as '[Non-Standard] + Reference.'

### 11.9.3. Deliverables

Delivery	Description
SAC	Final Statistical Analysis Complete

#### 11.9.4. Study Population Tables

Study Population Tables					
No.	Population	IDSL / Example Shell	Title	Programming Notes	Deliverable
Subject Disposition					
1.1.	Safety	ES1A	Summary of Participant Disposition for the Participant Conclusion Record	ICH E3, FDAAA, EudraCT	SAC
1.2.	Safety	SD1	Summary of Treatment Status and Reasons for Discontinuation of Study Treatment	ICH E3	SAC
1.3.	Safety	ES4	Summary of Participant Disposition at Each Study Epoch	ICH E3	SAC
1.4.	APE	ES6	Summary of Screening Status and Reasons for Screen Failure	Journal Requirements	SAC
Protocol Deviation					
1.5.	Safety	DV1	Summary of Important Protocol Deviations	ICH E3	SAC
1.6.	Safety	IE2	Summary of Inclusion/Exclusion Criteria Deviations		SAC
Population Analysed					
1.7.	Safety	SP1	Summary of Study Populations	IDSL	SAC
Demographic and Baseline Characteristics					
1.8.	Safety	DM3	Summary of Demographic Characteristics	ICH E3, FDAAA, EudraCT	SAC
1.9.	Safety	DM11	Summary of Age Ranges	EudraCT	SAC
1.10.	Safety	DM5	Summary of Race and Racial Combinations	ICH E3, FDA, FDAAA, EudraCT	SAC

Study Population Tables					
No.	Population	IDSL / Example Shell	Title	Programming Notes	Deliverable
Prior and Concomitant Medications					
1.11.	Safety	CM1	Summary of Concomitant Medications	ICH E3	SAC

### 11.9.5. Pharmacokinetic Tables

Pharmacokinetic: Tables					
No.	Population	IDSL / TST ID / Example Shell	Title	Programming Notes	Deliverable
Plasma					
2.1.	PK	PK01	Summary of Plasma Total Radioactivity Concentrations by Treatment and Time	Include un transformed concentrations	SAC
2.2.	PK	Refer to Programming Notes	Summary of Log Transformed Plasma Total Radioactivity Concentrations by Treatment and Time	Include log transformed concentrations use standard macro for sumstatsinrows for log transformed variable, present similar to example shell PK01 but present geometric mean and SD (Log) rather than mean and SD respectively.	SAC
2.3.	PK	PK03	Summary of Derived Plasma Total Radioactivity PK Parameters by Treatment	Include columns for parameter, period, treatment, N, n, arithmetic mean, 95% CI of arithmetic mean, standard deviation (SD), median, minimum and maximum.	SAC

Pharmacokinetic: Tables					
No.	Population	IDSL / TST ID / Example Shell	Title	Programming Notes	Deliverable
2.4.	PK	PK05	Summary of Log-Transformed Derived Plasma Total Radioactivity PK Parameters by Treatment	
Include columns for parameter, period, treatment, N, n, geometric mean, 95% CI of geometric mean, standard deviation (SD) of logged data, median, minimum, maximum and between subject geometric coefficient of variation (CVb (%)).
 
Refer to Section 11.4.3 for parameters that should be log transformed
 
refer to gsk2269557/pii115119/part_a/drivers/t_pk_sum_log (Table 4.3)
	SAC
2.5.	PK	PK01	Summary of Plasma [14C]-GSK2269557 Concentrations by Treatment and Time	Include untransformed concentrations	SAC
2.6.	PK	Refer to Programming Notes	Summary of Log Transformed Plasma [14C]-GSK2269557 Concentrations by Treatment and Time	Include log transformed concentrations use standard macro for sumstatsinrows for log transformed variable, present similar to example shell PK01 but present geometric mean and SD (Log) rather than mean and SD respectively.	SAC
2.7.	PK	PK03	Summary of Derived Plasma [14C]-GSK2269557 PK Parameters by Treatment	
Include columns for parameter, period, treatment, N, n, arithmetic mean, 95% CI of arithmetic mean, standard deviation (SD), median, minimum and maximum.
 
In addition to standard [14C]-GSK2269557 pk parameters include Clearance (CL(iv) and CLr) and volume (Vdss and Vc).
	SAC

Pharmacokinetic: Tables					
No.	Population	IDSL / TST ID / Example Shell	Title	Programming Notes	Deliverable
2.8.	PK	PK05	Summary of Log-Transformed Derived Plasma [14C]-GSK2269557 PK Parameters by Treatment	
Include columns for parameter, period, treatment, N, n, geometric mean, 95% CI of geometric mean, standard deviation (SD) of logged data, median, minimum, maximum and between subject geometric coefficient of variation (CVb (%)).
 
Refer to Section 11.4.3 for parameters that should be log transformed. In addition to standard [14C]-GSK2269557 pk parameters include Clearance (CL(iv) and CLr) and volume (Vdss and Vc).
 
refer to  gsk2269557/pii115119/part_a/drivers/t_pk_sum_log (Table 4.3)
	SAC
2.9.	PK	PK01	Summary of Plasma GSK2269557 Concentrations by Treatment and Time	Include untransformed concentrations	SAC
2.10.	PK	Refer to Programming Notes	Summary of Log Transformed Plasma GSK2269557 Concentrations by Treatment and Time	Include log transformed concentrations use standard macro for sumstatsinrows for log transformed variable, present similar to example shell PK01 but present geometric mean and SD (Log) rather than mean and SD respectively.	SAC
2.11.	PK	PK03	Summary of Derived Plasma GSK2269557 PK Parameters by Treatment	Include columns for parameter, period, treatment, N, n, arithmetic mean, 95% CI of arithmetic mean, standard deviation (SD), median, minimum and maximum.	SAC

Pharmacokinetic: Tables					
No.	Population	IDSL / TST ID / Example Shell	Title	Programming Notes	Deliverable
2.12.	PK	PK05	Summary of Log-Transformed Derived Plasma GSK2269557 PK Parameters by Treatment	
Include columns for parameter, period, treatment, N, n, geometric mean, 95% CI of geometric mean, standard deviation (SD) of logged data, median, minimum, maximum and between subject geometric coefficient of variation (CVb (%)).
 
Refer to Section 11.4.3 for parameters that should be log transformed
 
refer to gsk2269557/pii115119/part_a/drivers/t_pk_sum_log (Table 4.3)
	SAC
2.13.	PK	PK06	Summary of Oral and Inhaled Absolute Bioavailability	
Refer to Section 11.4.3 for parameters that should be log transformed.
 
Include PK Parameters: Inhaled F (0-∞), Inhaled F (0-t), Oral F (0-∞) and Oral F (0-t), Dose(Inhaled), Dose(iv) and Dose(Oral).
 
Note: Dose(iv) and Dose(Oral) is radiometric dose, Dose(Inhaled) is nominal
	SAC
2.14.	PK	PK06	Summary of Metabolic, Hepatic Extraction and Absorption Parameters	
Refer to Section 11.4.3 for parameters that should be log transformed.
 
Include PK Parameters: ML(iv), ML(po), Fg, EH and Fabs
	SAC

Pharmacokinetic: Tables					
No.	Population	IDSL / TST ID / Example Shell	Title	Programming Notes	Deliverable
2.15.	PK	[Non-Standard] Refer to Programming notes	Summary of Parent GSK2269557/Total Radioactivity Ratio for Cmax, AUC(0-24), AUC(0-∞) and AUC(0-t)	Include columns for: period, parent GSK2269557/total radioactivity ratio (GSK2269557/total radioactivity or 14C-GSK2269557/ total radioactivity), parameter (Cmax, AUC(0-24), AUC(0-∞) or AUC(0-t)), geometric mean for ratio, SD(log), 95% CI, median, minimum, maximum and between subject geometric coefficient of variation (CVb (%)).	SAC
2.16.	PK	[Non-Standard] Refer to Programming notes	Summary of Statistical Analyses for Parent GSK2269557/Total Radioactivity Ratio for Cmax, AUC(0-24), AUC(0-∞) and AUC(0-t)	Include columns for: period, parent GSK2269557/total radioactivity ratio (GSK2269557/total radioactivity or 14C-GSK2269557/ total radioactivity), parameter (Cmax, AUC(0-24), AUC(0-∞) or AUC(0-t)), estimate for ratio, SD(log) and 95% CI	SAC
Urine/Faeces					
2.17.	PK	PK02	Summary of Urinary and Faecal –Total Radioactivity Pharmacokinetic Parameters (Amount Excreted) by Treatment and Time	Include Ae(urine), Ae(faeces) and Ae(total).	SAC
2.18.	PK	PK02	Summary of Urinary and Faecal –Total Radioactivity Pharmacokinetic Parameters (Cumulative Amount Excreted) by Treatment and Time	Include cumulative Ae(urine), Cumulative Ae(faeces) and Cumulative Ae(total).	SAC
2.19.	PK	PK02	Summary of Urinary and Faecal –Total Radioactivity Pharmacokinetic Parameters (% of Dose Excreted) by Treatment and Time	Include Fe%(urine), Fe%(faeces) and Fe%(total).	SAC
2.20.	PK	PK02	Summary of Urinary and Faecal –Total Radioactivity Pharmacokinetic Parameters (Cumulative % of Dose Excreted) by Treatment and Time	Include cumulative Fe%(urine), Cumulative Fe%(faeces) and Cumulative Fe%(total).	SAC

### 11.9.6. Pharmacokinetic Figures

Pharmacokinetic: Figures					
No.	Population	IDSL / TST ID / Example Shell	Title	Programming Notes	Deliverable
Plasma					
2.1.	PK	PK16a	Individual Subject Plasma Total Radioactivity-time Plot (Linear and Semi-log) by Treatment	Linear and log plot on same page. Separate page per treatment. N (likely 6) lines for each treatment with legend to identify subjects Time = Planned time post dose (h) Include the LLOQ as a reference line and footnote  refer to GSK961081/mid201003/final/f_pk_21 (Table 2.1)	SAC
2.2.	PK	PK19	Arithmetic Mean (+SD) Plasma Total Radioactivity-time Plot (Linear and Semi-log) by Treatment	Linear and log plot on same page. Separate page per treatment. Time = Planned time post dose (h) Include the LLOQ as a reference line and footnote  refer to GSK961081/ mid201003/ final/ f_pk_22 (Table 2.2)	SAC
2.3.	PK	PK20	Median (Range) Plasma Total Radioactivity-time Plot (Linear and Semi-log) by Treatment	Linear and log plot on same page. Separate page per treatment. Time = Planned time post dose (h) Include the LLOQ as a reference line and footnote  refer to GSK961081/ mid201003/ final/ f_pk_23 (Table 2.3)	SAC

Pharmacokinetic: Figures					
No.	Population	IDSL / TST ID / Example Shell	Title	Programming Notes	Deliverable
2.4.	PK	PK16a	Individual Subject Plasma [14C]-GSK2269557 Concentration-time Plot (Linear and Semi-log) by Treatment	Linear and log plot on same page. Separate page per treatment. N (likely 6) lines for each treatment with legend to identify subjects Time = Planned time post dose (h) Include the LLOQ as a reference line and footnote  refer to GSK961081/mid201003/final/f_pk_21	SAC
2.5.	PK	PK19	Arithmetic Mean (+SD) Plasma [14C]-GSK2269557 Concentration-time Plot (Linear and Semi-log) by Treatment	Linear and log plot on same page. Separate page per treatment. Time = Planned time post dose (h) Include the LLOQ as a reference line and footnote  refer to GSK961081/ mid201003/ final/ f_pk_22	SAC
2.6.	PK	PK20	Median (Range) Plasma [14C]-GSK2269557 Concentration-time Plot (Linear and Semi-log) by Treatment	Linear and log plot on same page. Separate page per treatment. Time = Planned time post dose (h) Include the LLOQ as a reference line and footnote  refer to GSK961081/ mid201003/ final/ f_pk_23	SAC

Pharmacokinetic: Figures					
No.	Population	IDSL / TST ID / Example Shell	Title	Programming Notes	Deliverable
2.7.	PK	PK16a	Individual Subject Plasma GSK2269557 Concentration-time Plot (Linear and Semi-log) by Treatment	Linear and log plot on same page. Separate page per treatment. N (likely 6) lines for each treatment with legend to identify subjects Time = Planned time post dose (h) Include the LLOQ as a reference line and footnote  refer to GSK961081/mid201003/final/f_pk_21	SAC
2.8.	PK	PK19	Arithmetic Mean (+SD) Plasma GSK2269557 Concentration-time Plot (Linear and Semi-log) by Treatment	Linear and log plot on same page. Separate page per treatment. Time = Planned time post dose (h) Include the LLOQ as a reference line and footnote  refer to GSK961081/ mid201003/ final/ f_pk_22	SAC
2.9.	PK	PK20	Median (Range) Plasma GSK2269557 Concentration-time Plot (Linear and Semi-log) by Treatment	Linear and log plot on same page. Separate page per treatment. Time = Planned time post dose (h) Include the LLOQ as a reference line and footnote  refer to GSK961081/ mid201003/ final/ f_pk_23	SAC

Pharmacokinetic: Figures					
No.	Population	IDSL / TST ID / Example Shell	Title	Programming Notes	Deliverable
Urine and Faeces					
2.10.	PK	PK_F4	Individual Subject Absolute –Total Radioactivity Recovered (Amount Excreted) for Urine, Faeces and Total Excretion by Time and Treatment	Ae(urine), Ae(faeces), Ae(total). Linear scale only. Separate page per subject and treatment. 3 lines per plot with legend to identify Urine Faeces and Total Excretion Time = actual mid-point of collection post dose (h).  refer to GSK961081/ mid201003/ final/ f_pk_210	SAC
2.11.	PK	PK_F5	Arithmetic Mean Absolute –Total Radioactivity Recovered (Amount Excreted) for Urine, Faeces and Total Excretion by Time and Treatment	Ae(urine), Ae(faeces), Ae(total). Linear scale only. Separate page per Treatment. 3 lines per plot with legend to identify Urine Faeces and Total Excretion Time = actual mid-point of collection post dose (h).  refer to GSK961081/ mid201003/ final/ f_pk_212	SAC

Pharmacokinetic: Figures					
No.	Population	IDSL / TST ID / Example Shell	Title	Programming Notes	Deliverable
2.12.	PK	PK_F4	Individual Subject Cumulative –Total Radioactivity Recovered (Cumulative Amount Excreted) for Urine, Faeces and Total Excretion by Time and Treatment	Cumulative Ae(urine), Cumulative Ae(faeces), Cumulative Ae(total).  Linear scale only. Separate page per subject and treatment. 3 lines per plot with legend to identify Urine Faeces and Total Excretion Time = actual mid-point of collection post dose (h).  refer to GSK961081/ mid201003/ final/ f_pk_210	SAC
2.13.	PK	PK_F5	Arithmetic Mean Cumulative –Total Radioactivity Recovered (Cumulative Amount Excreted) for Urine, Faeces and Total Excretion by Time and Treatment	Cumulative Ae(urine), Cumulative Ae(faeces), Cumulative Ae(total).  Linear scale only. Separate page per Treatment. 3 lines per plot with legend to identify Urine Faeces and Total Excretion Time = actual mid-point of collection post dose (h).  refer to GSK961081/ mid201003/ final/ f_pk_212	SAC

Pharmacokinetic: Figures					
No.	Population	IDSL / TST ID / Example Shell	Title	Programming Notes	Deliverable
2.14.	PK	PK_F4	Individual Subject Absolute –Total Radioactivity Recovered (% of Dose) for Urine, Faeces and Total Excretion by Time and Treatment	Fe%(urine), Fe%(faeces), Fe%(total). Linear scale only. Separate page per subject and treatment. 3 lines per plot with legend to identify Urine Faeces and Total Excretion Time = actual mid-point of collection post dose (h). refer to GSK961081/ mid201003/ final/ f_pk_210	SAC
2.15.	PK	PK_F5	Arithmetic Mean Absolute –Total Radioactivity Recovered (% of Dose) for Urine, Faeces and Total Excretion by Time and Treatment	Fe%(urine), Fe%(faeces), Fe%(total). Linear scale only. Separate page per Treatment. 3 lines per plot with legend to identify Urine Faeces and Total Excretion Time = actual mid-point of collection post dose (h). refer to GSK961081/ mid201003/ final/ f_pk_212	SAC

Pharmacokinetic: Figures					
No.	Population	IDSL / TST ID / Example Shell	Title	Programming Notes	Deliverable
2.16.	PK	PK_F4	Individual Subject Cumulative –Total Radioactivity Recovered (Cumulative % of Dose) for Urine, Faeces and Total Excretion by Time and Treatment	Cumulative Fe%(urine), Cumulative Fe%(faeces), Cumulative Fe%(total). Linear scale only. Separate page per subject and treatment. 3 lines per plot with legend to identify Urine Faeces and Total Excretion Time = actual mid-point of collection post dose (h).  refer to GSK961081/ mid201003/ final/ f_pk_210	SAC
2.17.	PK	PK_F5	Arithmetic Mean Cumulative –Total Radioactivity Recovered (Cumulative % of Dose) for Urine, Faeces and Total Excretion by Time and Treatment	Cumulative Fe%(urine), Cumulative Fe%(faeces), Cumulative Fe%(total). Linear scale only. Separate page per Treatment. 3 lines per plot with legend to identify Urine Faeces and Total Excretion Time = actual mid-point of collection post dose (h).  refer to GSK961081/ mid201003/ final/ f_pk_212	SAC

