4. OBJECTIVES AND ENDPOINTS

Objectives	Endpoints
Primary	

 To determine total radioactivity (drug related material) in plasma following a single IV microtracer of [¹⁴C]-GSK2269557 (concomitant with an inhaled non-radiolabelled GSK2269557 dose) and a single oral dose of [¹⁴C]-GSK2269557. 	
 AUC(0-inf), AUC(0-t), Cmax, tmax, t_{1/2} of total drug-related material (radioactivity) in plasma.

 To determine the rate and extent of excretion of total radioactivity in urine and faeces and the total recovery of radioactivity following a single IV microtracer of [¹⁴C]-GSK2269557 (concomitant with an inhaled non-radiolabelled dose) and a single oral dose of [¹⁴C]-GSK2269557. 	
 Urinary and faecal cumulative excretion as a percentage of the total radioactive dose administered over time.
Secondary	

 To determine parent GSK2269557 concentration in plasma following a single IV microtracer of [¹⁴C]-GSK2269557 (concomitant with an inhaled non-radiolabelled GSK2269557 dose) and a single oral dose of [¹⁴C]-GSK2269557. 	
 AUC(0-inf), AUC(0-t), Cmax, tmax, and t_{1/2} of parent GSK2269557 and [¹⁴C]-GSK2269557¹ in plasma. Volume and clearance of parent [¹⁴C]-GSK2269557¹ after IV dose only.

 To estimate the absolute bioavailability of GSK2269557 following inhaled and oral administration. 	
 Oral and inhaled F (absolute bioavailability).

Objectives	Endpoints

 To evaluate the safety and tolerability of GSK2269557 after single IV, oral and inhaled doses in healthy participants. 	
 Incidence of adverse events Laboratory safety, electrocardiogram (ECG) and vital signs parameters.
Exploratory	

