The urine, faecal and total radioactivity parameters will be listed, summarised and plotted.

All pharmacokinetic data will be stored in the Archives, GlaxoSmithKline Pharmaceuticals, R&D. Production of the summaries, listings and figures of the plasma, urine and faeces data will be performed under the direct auspices of Clinical Statistics, GSK.

Further details regarding the tables, figures and listings to be produced for the study report will be given in the Reporting and Analysis Plan (RAP).

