**Table 2** **Derived Urine and Faeces Pharmacokinetic Parameters**

Parameter	Parameter Description
Ae[urine]	Total radioactivity recovered in the urine (Ae[urine]) calculated for each collection interval per subject and treatment period as:  Ae[urine]=(concentration in urine sample x collected sample weight) for each urine collection interval, eg 0-6, 6-24, 24-48, etc.
Cumulative Ae[urine]	Cumulative total radioactivity recovered in the urine (Cumulative Ae[urine]) calculated for each cumulative collection interval per subject and treatment period as:  Cumulative Ae[urine]= summation of Ae[urine] for each urine collection within the cumulative urine collection interval, eg 0-24, 0-48, etc.
Fe%[urine]	% of total dose excreted as total radioactivity (Fe%[urine]) for each collection interval per subject and treatment period, will be estimated as:  Fe%[urine]=(Ae[urine]) for each collection period)/Dose*100.  Where the dose is the radiolabelled [  C]-GSK2269557, that is in period 1 radiometric iv dose, in period 2 radiometric oral dose
Cumulative Fe%[urine]	Cumulative % of total dose excreted as total radioactivity (Cumulative Fe%[urine]) for each cumulative collection interval per subject and treatment period, will be estimated as:  Cumulative Fe%[urine]=summation of Fe%[urine] for each urine collection within the cumulative urine collection interval, eg 0-24, 0-48, etc.

Parameter	Parameter Description
Ae[faeces]	
Total radioactivity recovered in the faeces (Ae[faeces]) calculated for each collection interval per subject and treatment period as
 $Ae[\text{faeces}] = (\text{concentration in faecal homogenate aliquot analysed} \times \text{weight of homogenate aliquot analysed}) \times (\text{total homogenate weight} / \text{collected sample weight})$ 
for each faecal collection interval, eg 0-24, 24-48, etc

Cumulative Ae[faeces]	
Cumulative total radioactivity recovered in the faeces (Cumulative Ae[faeces]) calculated for each cumulative collection interval per subject and treatment period as
 $\text{Cumulative Ae}[\text{faeces}] = \text{summation of Ae}[\text{faeces}]$ 
for each faecal collection within the cumulative faecal collection interval, eg 0-24, 0-48, etc

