Fe%[faeces]	
% of total dose excreted as total radioactivity (Fe%[faeces]) for each collection interval per subject and treatment period will be estimated as:
 $Fe\%[\text{faeces}] = (Ae[\text{faeces}] \text{ for each collection period}) / \text{Dose} * 100.$ 
Where the dose is the radiolabelled [C]-GSK2269557, that is in period 1 radiometric iv dose, in period 2 radiometric oral dose

Cumulative Fe%[faeces]	
Cumulative % of total dose excreted as total radioactivity (Cumulative Fe%[faeces]) for each cumulative collection interval per subject and treatment period will be estimated as:
 $\text{Cumulative Fe\%}[\text{faeces}] = \text{summation of Fe\%}[\text{faeces}]$ 
for each faecal collection within the cumulative faecal collection interval, eg 0-24, 0-48, etc.

Ae[total]	
Total radioactivity recovered in total excretion (sum of urine and faecal excretion), Ae[total] will be estimates by collection interval for each subject and treatment period as:
 $Ae[\text{total}] = Ae[\text{urine}] + Ae[\text{faeces}]$
Cumulative Ae[total]	
Total radioactivity recovered in total excretion (sum of urine and faecal excretion), cumulative Ae[total] will be estimates by cumulative collection interval per subject and treatment period as:
 $\text{Cumulative Ae}[\text{total}] = \text{summation of Ae}[\text{total}]$ 
for each total excretion collection within the cumulative total excretion collection interval, eg 0-24, 0-48, etc

Fe%[total]	
% of total dose excreted as total radioactivity (Fe%[total]) for each collection period will be estimated for each subject and treatment period as:
 $Fe\%[\text{total}] = Fe\%[\text{urine}] + Fe\%[\text{faeces}]$
Cumulative Fe%[total]	
Cumulative % of total dose excreted as total radioactivity (Cumulative Fe%[total]) for each cumulative collection period will be estimated for each subject and treatment period as:
 $\text{Cumulative Fe\%}[\text{total}] = \text{Cumulative Fe\%}[\text{urine}] + \text{Cumulative Fe\%}[\text{faeces}]$ 
for each total excretion collection within the cumulative total excretion collection interval, eg 0-24, 0-48, etc

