### **8.2.2. Summary Measure**

A primary objective is to determine total radioactivity (drug related material) in plasma following a single IV microtracer of [14C]-GSK2269557 (concomitant with an inhaled non-radiolabelled GSK2269557 dose) and a single oral dose of [14C]-GSK2269557. To assess this, the plasma PK parameters: AUC (0-inf), AUC (0-t), AUC (0-24), %AUCex, Cmax, tmax, t1/2 of total drug-related material (radioactivity) will be summarised and listed.

The additional primary objective is to determine the rate and extent of excretion of total radioactivity in urine and faeces and the total recovery of radioactivity following a single IV microtracer of [14C]-GSK2269557 (concomitant with an inhaled non-radiolabelled dose) and a single oral dose of [14C]-GSK2269557. To assess this, the PK parameters: Ae and Fe% will be summarised and listed for urine faeces and total (Urine + Faeces).

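### The four cumulative-excretion figures (SAP Figures 2.12, 2.13, 2.16 and 2.17) plot each sum at the mid-point of its collection instead of the end, so 24-h blocks are drawn 12 h early (minor, display only)

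*SAP*

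**What the plan says.** The protocol (Section 4) makes this a primary endpoint: "Urinary and faecal cumulative excretion as a percentage of the total radioactive dose administered over time". The matching objective covers the rate as well as the extent of excretion. Protocol Section 10.3.1 commits to plotting it: "The urine, faecal and total radioactivity parameters will be listed, summarised and plotted".

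SAP Table 2 defines the cumulative quantities as running sums. For urine the definition is "summation of Ae[urine] for each urine collection within the cumulative urine collection interval, eg 0-24, 0-48, etc". For the total (urine plus faeces) it is "for each total excretion collection within the cumulative total excretion collection interval, eg 0-24, 0-48, etc".

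SAP Section 11.9.6 lists eight excretion figures:

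- Figures 2.10, 2.11, 2.14 and 2.15 show per-interval values. The note for Figure 2.10 begins "Ae(urine), Ae(faeces), Ae(total). Linear scale only. Separate page per subject and treatment".
- Figures 2.12 and 2.13 show cumulative amount, and Figures 2.16 and 2.17 show cumulative percentage of dose.

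All eight carry the same time rule. For Figures 2.12, 2.13 and 2.16 it reads "3 lines per plot with legend to identify Urine Faeces and Total Excretion Time = actual mid-point of collection post dose (h". For Figure 2.17 it reads "legend to identify Urine Faeces and Total Excretion Time = actual mid-point of collection post dose (h".

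**The concern.** A per-interval amount has no single time, so its mid-point is a sensible place to draw it. A cumulative value is different: the 0-48 h sum includes material collected up to 48 h, yet the note places it at 36 h. The cumulative figures also cite the same reference programs as their per-interval counterparts, so the rule may simply have been carried across, though the SAP does not say so.

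What is at stake is how the plots read. Figures 2.16 and 2.17 are the planned pictures of a primary endpoint expressed over time. A reader who takes a time or a percentage from a curve gets a time that is too early or a percentage that is too high wherever the curve is still rising.

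**Working it through.** **Inputs.** The collection schedule is in the footnotes to Protocol Section 2 and is the same in both periods to 168 h. Urine is collected over 0-6 h, 6-24 h and then 24-h blocks. Faeces are collected in 24-h blocks from 0 h. The time rule is from SAP Section 11.9.6 and the definitions are from SAP Table 2.

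**Step 1: shift.** Shift = interval end minus mid-point = half the length of the last interval in the sum. Times are nominal, because the rule uses actual times.

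| Cumulative value | Last interval | Drawn at | Interval end | Shift |
|---|---|---|---|---|
| Urine 0-6 h (if plotted) | 0-6 h | (0+6)/2 = 3 h | 6 h | 3 h |
| Urine 0-24 h | 6-24 h | (6+24)/2 = 15 h | 24 h | 9 h |
| Faeces 0-24 h | 0-24 h | (0+24)/2 = 12 h | 24 h | 12 h |
| Either, 0-48 h | 24-48 h | (24+48)/2 = 36 h | 48 h | 12 h |
| Either, 0-168 h | 144-168 h | (144+168)/2 = 156 h | 168 h | 12 h |

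The 0-6 h row is conditional because the cumulative intervals that Table 2 gives as examples start at 0-24 h.

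**Step 2: agreement between curves on day 1.** The 0-24 h value falls at 15 h for urine and 12 h for faeces. The 0-24 h total has a nominal mid-point of 12 h. At 12 h the urine curve has not yet reached its 0-24 h value, so the plotted total is not the sum of the two curves beside it.

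**Step 3: common time in the mean figures.** Actual mid-points can differ between participants, so a mean plotted under this rule has no common time. This affects mean Figures 2.13 and 2.17 and equally the per-interval mean Figures 2.11 and 2.15. The SAP's mean plasma figures use planned time.

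**Step 4: is there an override?** SAP Section 11.4.2 makes planned time the default for figures unless something else is stated, and these notes state something else. That is a permitted exception, not a contradiction, but it does not supply the interval end. Reading the rule as the mid-point of the whole cumulative interval makes the shift larger: 24 h for 0-48 h and 84 h for 0-168 h.

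**Step 5: illustration in percentage points (assumed model).** Assume smooth first-order excretion without lag, reaching 90% of dose by one route: F(t) = 90 x (1 - 2^(-t/h)). Neither the model, the 90% nor the half-lives h are in the documents. On a faeces curve, the value read at 24 h lies halfway between the points drawn at 12 h and 36 h, so it is (F(24) + F(48))/2. On a urine curve it is F(24) + (9/21) x (F(48) - F(24)).

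| h | True F(24) | Faeces curve reads | Urine curve reads |
|---|---|---|---|
| 12 h | 67.50 | 75.94 (+8.4) | 74.73 (+7.2) |
| 24 h | 45.00 | 56.25 (+11.3) | 54.64 (+9.6) |
| 48 h | 26.36 | 35.68 (+9.3) | 34.35 (+8.0) |
| 96 h | 14.32 | 20.34 (+6.0) | 19.48 (+5.2) |

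The error scales with the percentage recovered by the route: a urine curve ending at 20% of dose would be off by at most 9.64 x 20/90 = 2.1 points at 24 h. Late in collection it is small. Once less than 1% of dose is excreted per day, it is below (12/24) x 1% = 0.5 point.

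**The case against.** **The endpoint is reported correctly elsewhere.** SAP Section 8.2.2 assesses the excretion objective without the figures: "To assess this, the PK parameters: Ae and Fe% will be summarised and listed for urine faeces and total (Urine + Faeces". Table 2.20 gives cumulative percentage by treatment and time, no time-to-percentage parameter is planned, and the discharge rule uses 24-h counting results. This stands, and it is why the point is minor. A reader might infer that the recovery estimate or the primary result is wrong. The documents do not support that, because no planned table, listing or parameter uses the plotted time.

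**Faecal values may be reached before the block ends.** A reader might take the 12 h as the distance from the moment the value was reached. For faeces that is not supported. The inclusion criteria ask for an average of at least one bowel movement a day. If, as an assumption, one stool falls uniformly within a 24-h block, the value is reached at 12 h on average. With two stools, the last comes on average at 24 x 2/3 = 16 h. Against that moment the mid-point is 0 to 4 h early. This stands as a limit on the faecal shift. The interval end is still the first scheduled time at which the sum is certain to be complete.

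**The percentage-point errors are modelled.** Smooth excretion without lag is a poor description of discrete stools. This stands: the second table in the working is an illustration and not an estimate for this compound.

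**The shells and reference programs are not in the document.** The code, or an axis label, might differ from the note. That is possible, but the written specification would still need correcting.

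**Conclusion.** The time rule is wrong for Figures 2.12, 2.13, 2.16 and 2.17 as written. The effect is minor and confined to display. Relative to the scheduled interval end, points sit 12 h early for 24-h blocks, 9 h early for the 0-24 h urine value and 3 h early for a 0-6 h urine value. These shifts rest only on the schedule and the stated rule. They make excretion look faster than measured in the plots of a primary endpoint, with the reservation for stool timing.

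No percentage-point error can be claimed for this trial, because its size depends on the excretion model assumed. Nor should the shift be expressed as an error in the time to half of final recovery. Under the assumed model with a 48-h half-life, 45% of dose is reached at 48 h and reads 36 h, but 45% is half of the assumed eventual 90%. Recovery by 168 h would be 82.0%. Half of that, 41.0%, is reached at 42.1 h and reads about 30.9 h on a faeces curve.

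**What to change.** In SAP Section 11.9.6:

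- Figures 2.12 and 2.16 (individual): set Time to the actual end of the collection interval.
- Figures 2.13 and 2.17 (mean): set Time to the planned end of the interval.
- All four: plot the cumulative total only where urine and faecal intervals both close (24 h, 48 h and so on). The intervals given as examples in Table 2 already suggest this, so the note only makes it explicit.
- Figures 2.10 and 2.14: keep the actual mid-point.
- Figures 2.11 and 2.15 (mean): keep mid-points but use the planned mid-point, so that each mean has a common time.

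The cost is an edit to six programming notes, four cumulative and two per-interval mean. Data collection, tables and listings do not change. The downside is that the cumulative figures need their own time variable and can no longer share the rule used for the per-interval figures.
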